Study treatment	
 CFZ533 150 mg or placebo Liquid in vial for injection 
 CFZ533 10 mg/kg administered by intravenous infusion placebo administered by intravenous infusion 
Intravenous infusion will be administered at Days 1, 15, 29, 57, 85, 113, and 141

Pharmacokinetic assessments	
 Free CFZ533 in plasma
Efficacy/PD assessments	
 Urinary protein creatinine ratio (UPCR) Total soluble CD40 (target engagement) in plasma
Key safety assessments	
 Adverse events/Serious adverse events Vital signs ECG evaluation Standard hematology and chemistry evaluations Immunogenicity
Other assessments	Commercially Confidential Information

Data analysis	
The primary variable is the ratio from baseline in urinary protein creatinine ratio (UPCR) at Week 25, using first morning void. This ratio will be log transformed prior to the analysis. A repeated measures mixed model will be fitted with factors for treatment group (CFZ533 or placebo) and visit (e.g. Week 5, 9, 13 etc.). The model will also include a factor for the prednisone dose-equivalent at baseline (≤ 10 mg, >10 mg), which is a stratification factor for the randomization. Log-transformed baseline UPCR will be included in the model as a covariate along with the interactions between visit and all of the fixed effects. A normal errors model will be assumed with an unstructured covariance matrix to account for the correlation within subjects.
 
At each of the visits, the difference between the CFZ533 and placebo group will be estimated (along with its corresponding 95% confidence interval) and then back-transformed to provide an estimate of the ratio between treatment groups.
 
Descriptive statistics will be provided for the safety data (e.g. AEs, vital signs, ECGs, hematology and chemistry evaluations etc.). For serious adverse events and adverse events of special interest, statistical analyses comparing the event rates in the two treatment groups will be performed.

Key words	CFZ533, anti-CD40, moderately active lupus nephritis

1 Introduction

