1.3.2 Human pharmacokinetic and pharmacodynamic data

1.3.2.1 Study CCFZ533X2101

In healthy subjects as well as in patients with rheumatoid arthritis, after single IV or SC administration, CFZ533 PK profiles were consistent with target mediated disposition resulting in non-linear PK profiles and more rapid clearance when CD40 receptor occupancy dropped below approximately 90%.

Despite some inter-individual variability in the PK profiles from the Chinese subjects, the disposition of CFZ533 in Chinese subjects was generally similar as for non-Chinese subjects, and the target engagement was also similar (about 4 weeks) after 3 mg/kg IV CFZ533. At this dose level, similar PK/PD profiles were demonstrated through free CFZ533 profiles in plasma, CD40 occupancy on peripheral B cells measuring free CD40 and total CD40, and total sCD40 concentrations in plasma.

In patients with rheumatoid arthritis at 10 mg/kg IV, as measured by free CD40 on whole blood B cells compared to mean pre-dose, and total sCD40 profiles in plasma, full CD40 occupancy was generally maintained for 8 weeks. At 30 mg/kg IV, PK and total sCD40 profiles in plasma are consistent with a duration of target engagement of 16 weeks.

In healthy subjects CD40 engagement by CFZ533 generally led to a decrease in total CD40 on peripheral B cells by about 50%, tracking CD40 occupancy on B cells as measured by free CD40 on B cells. This is likely due to internalization and/or shedding of the membrane bound

CD40 upon binding to CFZ533. In patients with rheumatoid arthritis the decrease in total CD40 on peripheral B cells was not confirmed.

The relationship between CFZ533 in plasma and CD40 occupancy on whole blood B cells (free CD40 on B cells) was defined, and CFZ533 concentrations of 0.3-0.4 μ g/mL were associated with full (defined as $\geq 90\%$) CD40 occupancy on whole blood B cells.

More generally, non-specific and specific elimination pathways have been identified for CFZ533. The non-specific and high capacity pathway mediated by FcRn receptors is commonly shared by endogenous IgGs. The specific target mediated disposition of CFZ533 led to the formation of CFZ533-CD40 complexes that were partially internalized (with subsequent lysosomal degradation) and/or shed from the membrane. Target-mediated processes resulted in saturable and nonlinear disposition of CFZ533. The formation of CFZ533-CD40 complexes was dose/concentration-dependent, with saturation occurring at high concentrations of CFZ533.

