Overall, the disposition of CFZ533 is dependent on the relative contribution of the specific (target mediated) and non-specific elimination pathways to the overall clearance of CFZ533. Nonlinear PK behavior was observed when CFZ533 concentrations were lower than that of the target, while at higher concentrations with CD40 receptors being saturated, the non-specific pathways predominate and the elimination of CFZ533 was linear.

As expected for a typical IgG1 antibody targeting a membrane bound receptor and demonstrating target mediated disposition, the extent of exposure of CFZ533 (AUClast) increased more than the increase in dose (hyper-proportionality). Consequently, this is expected to be associated with a decrease in the volume of distribution and clearance of CFZ533 at higher doses.

One subject at 1 mg/kg IV CFZ533 (1 week full CD40 occupancy) developed specific antibodies to CFZ533 detected 6 weeks after CFZ533 plasma concentrations were below the limit of quantification, and definitively too low to block any CD40 pathway-relevant effects in tissue. The presence of anti-drug antibodies (ADAs) in this subject did not compromise exposure, and was not associated with an immune related safety signal. This corresponds to an ADA incidence of 2% in this study.

A single dose of 3 mg/kg (IV and SC) of CFZ533 transiently suppressed anti-KLH responses to the first KLH immunization, at CFZ533 concentrations corresponding to full ($\geq 90\%$) receptor occupancy (for about 3-4 weeks). Anti-KLH primary responses were detected in all subjects as CFZ533 concentration, and accompanying receptor occupancy, declined. All subjects were able to mount recall responses to a second KLH immunization (administered after loss of receptor occupancy was anticipated).

Data suggest that CD40 engagement by CFZ533 prevented recombinant human CD154 (rCD154) mediated B cell activation in human whole blood. The rCD154-induced-CD69 expression on B cells was generally suppressed during a period corresponding to full CD40 occupancy on B cells. When CD40 occupancy was incomplete, the functional activity of rCD154 was restored.

There was no evidence of any effect of CFZ533 on immunophenotyping data.

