3.1 Study design

This is an exploratory, randomized (2:1 active:placebo), subject- and investigator-blind, placebo-controlled, multicenter study evaluating the safety, tolerability, pharmacokinetics and preliminary efficacy of multiple doses of 10 mg/kg CFZ533 administered intravenously (IV) in lupus nephritis patients.

The study will randomize approximately 60 subjects with moderately active lupus nephritis. The study comprises two periods. The 24-week treatment period will be followed by a 24-week safety follow-up period (starting on Day 169). The duration of the study (including a screening period of up to 4 weeks) for each subject will be approximately 53 weeks. The investigational drug or placebo will be administered on top of standard of care therapy for lupus nephritis. The randomization will be stratified by baseline daily dose equivalent of prednisone (≤ 10 mg, > 10 mg). Patients who do not receive corticosteroids at baseline will be included in the ≤ 10 mg stratum.

Subjects will be screened within 29 days of the first study drug infusion. Eligibility will be confirmed at the baseline visit within one week before the first dose. All baseline safety evaluation results must be available prior to dosing, and meeting eligibility criteria. Eligible subjects will enter the treatment period, and will be randomized at a 2:1 ratio to receive treatment with either CFZ533 or placebo. Subjects will receive the intravenous infusion on Day 1 within seven days of the baseline visit, followed by PK, PD, and safety assessments until one hour after completed infusion.

Comercially Confidential Information

All infusions will take place in a monitored facility with assessment of vital signs ahead of the infusion. Subjects will be discharged 1 hour post-dose following satisfactory review of safety data (AE events, vital signs) by the Investigator.

Each patient will come to the study site for the follow-up evaluations on Day 169, Day 197, Day 225, Day 253, Day 281, Day 309, and Day 337, respectively. Patients should remain on their standard of care therapies. Dose of standard of care (SoC) therapies (see eligibility criteria and permitted co-medications) must remain unchanged during the study. However, in case of SoC related toxicities, doses of concomitant medications may be adjusted at the investigator's discretion.

Comercially Confidential Information

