8.7 Pharmacokinetics

PK blood samples will be collected at the timepoints defined in the [Assessment schedule](#) (Section 8.1). Follow instructions outlined in the Site Operations Manual regarding sample collection, numbering, processing and shipment.

Commercially Confidential Information

Pharmacokinetic (PK) samples will be obtained from all patients (CFZ533 and placebo-treated) to maintain blinding, but the analysis (free CFZ533 concentration in plasma) will only be conducted for CFZ533 treated patients.

Commercially Confidential Information

For standard pharmacokinetic abbreviations and definitions see the list provided at the beginning of this protocol. PK samples will be collected at pre-dose and 1-hour after the end of the intravenous infusion on dosing days, and at time of the scheduled visit during the Follow-up Period.

The following pharmacokinetic parameters will be determined for free CFZ533 in plasma (i) C_{trough,ss} or C_{min,ss}, and C_{max,ss} will be directly derived from the bioanalytical data and listings, and (ii) AUClast from the last dose at Day 141 will be determined using the actual recorded sampling times and non-compartmental methods with Phoenix WinNonlin (Version 8.0 or higher). The linear trapezoidal rule will be used for AUClast calculation.

No other parameters (e.g. clearance, volume of distribution, or half-life) will be derived using non-compartmental analysis (NCA). The pharmacokinetics of CFZ533 is non-linear and characterized by target-mediated disposition where CD40 binding by CFZ533 is leading to CFZ533 elimination (this includes receptor-mediated endocytosis by the membrane bound CD40, and subsequent metabolism of the CFZ533-CD40 complexes). As such, it is expected that:

- The amount of drug-target complex does influence the pharmacokinetics of CFZ533,
- Tissue metabolism may have a significant impact on the disposition of CFZ533 (the volume of distribution will be dependent on clearance),
- The volume of distribution may not be accurately inferred from plasma concentration alone, and the values for the volume of distribution obtained from a NCA may be incorrect,
- Volume of distribution and clearance parameters (as inferred from NCA analysis) would decrease when the dose increases.

The NCA approach is not appropriate due to violations of the assumptions that the disposition of the drug is linear, and that the elimination is from sites that are in rapid equilibrium with blood.

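### The linear trapezoidal rule across 28-day gaps overstates AUClast after the Day 141 dose; linear-up/log-down comes closer with the same samples

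*Protocol*

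**What the plan says.** AUClast of free CFZ533 is a secondary PK parameter (protocol 2.2).

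- **Rule.** Protocol 8.7: "The linear trapezoidal rule will be used for AUClast calculation". SAP 5.1 says the same.
- **Window.** "AUClast from the last dose at Day 141 will be determined using the actual recorded sampling times" (protocol 8.7).
- **Dosing.** "Intravenous infusion will be administered at Days 1, 15, 29, 57, 85, 113, and 141" (protocol summary).
- **Sampling.** PK samples are taken before dosing and "1-hour after the end of the intravenous infusion on dosing days, and at time of the scheduled visit during the Follow-up Period" (protocol 8.7). Protocol 3.1 lists "follow-up evaluations on Day 169, Day 197, Day 225, Day 253, Day 281, Day 309, and Day 337, respectively". No sample is therefore planned between 1 hour after the Day 141 infusion and Day 169, and later samples are 28 days apart. Table 8-1 is hard to read in the copy reviewed, so this rests on the text of 8.7 and 3.1.
- **Shape of the curve.** Protocol 1.3.2.1: "at higher concentrations with CD40 receptors being saturated, the non-specific pathways predominate and the elimination of CFZ533 was linear". It also reports "more rapid clearance when CD40 receptor occupancy dropped below approximately 90" percent.

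The list of PK definitions allows concentrations below the limit of quantification to be treated as zero.

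**The concern.** While elimination is linear, concentration falls roughly exponentially, and an exponential is convex. A straight line between two points on a convex curve lies above it, so each such trapezoid is too large. The excess depends on how far the concentration falls within the interval, and 28 days is long enough for a large fall.

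The bias is not a constant factor. It is larger in patients with faster clearance, who have the smaller true areas, so differences in exposure between patients are compressed. Protocol 3.3.1 itself cites an association of proteinuria with higher clearance for another antibody in SLE, and this population is selected for proteinuria. At stake are the reported level of exposure, comparisons between patients, and comparisons with studies sampled more densely.

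**Working it through.** The visible documents give no AUC, half-life or bias figure, so there is nothing to reproduce first.

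**Step 1. One 28-day gap, exponential decline.** With k = ln 2 / half-life and T = 28 days, linear area / true area = (kT/2) × coth(kT/2). The log rule is exact here. At a 10-day half-life, kT/2 = 0.970 and the ratio is 1.30.

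| Assumed half-life (days) | 5 | 7 | 10 | 14 | 18 | 21 | 28 |
|---|---|---|---|---|---|---|---|
| Linear / true | 2.02 | 1.57 | 1.30 | 1.16 | 1.10 | 1.07 | 1.04 |

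**Step 2. Calibration.** Protocol 1.3.2.1 gives 0.3-0.4 µg/mL for full occupancy and engagement of about 4, 8 and 16 weeks after single IV doses of 3, 10 and 30 mg/kg. Protocol 3.6.2.2 gives 14 weeks for the effect to persist after the last dose, and 5.2 gives a washout of about 16 weeks. The model has two compartments with linear plus Michaelis-Menten elimination and uses the protocol's dosing and sampling days. Assumed: 70 kg, 1-hour infusion, threshold 0.35 µg/mL.

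**Step 3. One calibrated fit in full.** V1 2.7 L, V2 2.5 L, Q 0.5 L/day, CL 0.098 L/day, Vmax 7.01 mg/day, Km 1.0 mg/L. Time to threshold is 26 days after 3 mg/kg, 60 after 10 mg/kg, 106 after 30 mg/kg and 88 after Day 141. Predicted concentrations are 374.4 (1 hour post-infusion), 117.7 (Day 169), 43.3 (Day 197) and 1.4 µg/mL (Day 225). Linear area = Δt(C1+C2)/2; log area = Δt(C1−C2)/ln(C1/C2). Areas are in µg·day/mL.

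| Interval | True | Linear (ratio) | Log (ratio) |
|---|---|---|---|
| 1 h to Day 169 | 5193 | 6870 (1.32) | 6194 (1.19) |
| Day 169-197 | 2166 | 2254 (1.04) | 2083 (0.96) |
| Day 197-225 | 548 | 625 (1.14) | 340 (0.62) |
| Total | 7907 | 9749 (1.23) | 8617 (1.09) |

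The unsampled first gap holds 66% of the area and most of the error. In the last interval, where target-mediated loss sets in, the log rule is 38% too low, but that interval is 7% of the area.

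**Step 4. Range.** Six such fits gave +14% to +29% for the linear rule and +1% to +14% for linear-up/log-down. A random sweep (V1 2.5-4 L, V2 0.8-4 L, Q 0.15-1.2 L/day, quantification limit 0.05 µg/mL) kept 552 of 3770 parameter sets. The criteria were time to threshold of 45-70 days after 10 mg/kg, 95-130 days after 30 mg/kg, and 70-125 days after Day 141.

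| | Linear | Linear-up/log-down |
|---|---|---|
| Median error | +17% | +5% |
| 5th-95th percentile | +7% to +50% | 0% to +18% |
| Full range | +4% to +102% | −3% to +28% |
| Median, first gap only | +24% | +12% |
| Median, 194 sets taking ≥95 days after Day 141 | +11% | +4% |

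The linear rule overstated in every set, by more than 10% in 81% of sets and by more than 20% in 41%. Linear-up/log-down was closer to the true area in all 552.

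**Step 5. Other assumptions.** A second sweep with different assumed parameter ranges (311 sets) gave larger medians, +31% against +12%, and the same ranking in every set.

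**The case against.** Both rules are conventional, and the plan states its choice consistently in two places. AUClast is summarised descriptively, in CFZ533-treated patients only and under one regimen. The documents themselves call non-compartmental analysis unsuitable for this drug, decline to derive clearance, volume or half-life from it, and allow population modelling (protocol 11.5.3, SAP 5.3). Log-down does not supply the missing early samples, and its own error varies between patients and can change sign. All of this stands. It limits the importance of the point but does not change which rule is closer.

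Three stronger readings are tempting and are not supported.

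- *AUClast could be nearly tripled.* Generic antibody parameters (CL 0.2-0.4 L/day, V1 3 L, Vmax 0-15 mg/day, Km 0.5 mg/L) give +32% to +188% for the linear rule. None of 24 combinations over these ranges matches the documented durations together. With saturable elimination they reach the threshold 36-87 days after 30 mg/kg, against 16 weeks (112 days) in the protocol. Those with errors of +170% or more reach it 19-27 days after 10 mg/kg, against 8 weeks.
- *Target-mediated loss adds to the overstatement by making the curve more convex.* Faster fractional loss at low concentration instead bends the curve towards a straight line. The argument rests on the exponential phase alone.
- *Log-down makes AUClast accurate.* It still overstates the first gap and can understate the late interval, as step 3 shows.

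**Conclusion.** The point holds as a minor improvement. The direction of the bias follows from the protocol's own description of elimination at saturation. The ranking of the two rules held in every document-calibrated model tried. The size is conditional on parameters the visible text does not give: over one gap, under 10% if the effective half-life is about 18 days or longer, and about 30% or more at 10 days or shorter. The calibrated medians are +17% against +5%, or +11% against +4% for models nearest the 14 to 16 week durations; other assumed ranges gave +31% against +12%. An unconditional claim of substantial overstatement is therefore not established.

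The effect is confined to descriptive exposure summaries and to comparisons of exposure between patients or studies. No visible hypothesis test, treatment-arm comparison or sample size depends on AUClast.

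**What to change.** In protocol 8.7 and SAP 5.1, specify the linear-up/log-down trapezoidal method for AUClast, keeping the linear rule for any interval that ends in a value below quantification set to zero, where a logarithm cannot be taken.

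Add a sentence on what remains: nothing is sampled between 1 hour after the Day 141 infusion and Day 169, and log-down can understate the late target-mediated interval. The population modelling already permitted can supply a model-based area if accurate exposure is needed.

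**Cost.** No extra sample or visit is needed. The protocol wording must go through the written amendment process (protocol 13.1), so the change is small but not free. Comparability with any earlier AUClast computed by the linear rule may be lost; the visible text does not say which rule earlier studies used. Reporting the linear-rule value as a supplement covers this.

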8.8 Other assessments

Commercially Confidential Information

Commercially Confidential Information

Commercially Confidential Information

Commercially Confidential Information

9 Safety monitoring

9.1 Adverse events

An adverse event (AE) is any untoward medical occurrence (i.e., any unfavorable and unintended sign [including abnormal laboratory findings], symptom or disease) in a subject after *providing written informed consent* for participation in the study until the end of study visit. Therefore, an AE may or may not be temporally or causally associated with the use of a medicinal (investigational) product.

In addition, all reports of intentional misuse and abuse of the study treatment are also considered an adverse event irrespective if a clinical event has occurred. See [Section 9.6](#) for an overview of the reporting requirements.

The occurrence of adverse events must be sought by non-directive questioning of the subject at each visit during the study. Adverse events also may be detected when they are volunteered by the subject during or between visits or through physical examination finding, laboratory test finding, or other assessments.

Abnormal laboratory values or test results constitute adverse events only if they fulfill at least one of the following criteria:

- they induce clinical signs or symptoms,
- they are considered clinically significant,
- they require therapy.

Clinically significant abnormal laboratory values or test results should be identified through a review of values outside of normal ranges/clinically notable ranges, significant changes from baseline or the previous visit, or values which are considered to be non-typical in patients with underlying disease. Investigators have the responsibility for managing the safety of individual subject and identifying adverse events. Alert ranges for liver and kidney related events are included in [Appendix 1](#) and [Appendix 2](#), respectively.

All adverse events should be recorded on the Adverse Events CRF under the signs, symptoms or diagnosis associated with them, and accompanied by the following information:

1. The severity grade
 - mild: usually transient in nature and generally not interfering with normal activities
 - moderate: sufficiently discomforting to interfere with normal activities
 - severe: prevents normal activities
2. its relationship to the study treatment
 - Yes or
 - No
3. its duration (start and end dates) or if the event is ongoing an outcome of not recovered/not resolved must be reported
4. whether it constitutes a SAE (see [Section 9.3](#) for definition of SAE) and which seriousness criteria have been met
5. Action taken regarding investigational treatment

All adverse events must be treated appropriately. Treatment may include one or more of the following:

- no action taken (e.g. further observation only)
- investigational treatment dosage increased/reduced
- investigational treatment interrupted/withdrawn
- concomitant medication or non-drug therapy given
- hospitalization/prolonged hospitalization (see [Section 9.3](#) for definition of SAE)

6. its outcome (not recovered/not resolved; recovered/resolved; recovering/resolving, recovered/resolved with sequelae; fatal; or unknown). Information about common side effects already known about the investigational drug can be found in the Investigator's Brochure (IB) or will be communicated between IB updates in the form of Investigator Notifications. Once an adverse event is detected, it must be followed until its resolution or until it is judged to be permanent, and assessment should be made at each visit (or more frequently, if necessary) of any changes in severity, the suspected relationship to the investigational drug, the interventions required to treat it, and the outcome.

The investigator must also instruct each subject to report any new adverse event (beyond the protocol observation period) that the subject, or the subject's personal physician, believes might reasonably be related to study treatment. This information must be recorded in the investigator's source documents; however, if the AE meets the criteria of an SAE, it must be reported to Novartis.

Adverse events potentially leading to treatment discontinuation should also be assessed using the CTCAE grading, version 4.03. CTCAE grading will not be recorded into the eCRF.

